2.1 Trial medication

Neumifil is a first-in-class, multivalent, glycan-targeting carbohydrate binding module (CBM). It is being developed as a nasal formulation to treat viral respiratory tract infections (RTIs), including those caused by SARS-CoV-2.

2.2 Objectives

2.2.1 Primary objectives

Part A

- To assess the safety and tolerability of single-ascending intranasal doses of Neumifil in healthy subjects.

Part B

- To assess the safety and tolerability of multiple-ascending intranasal doses of Neumifil in healthy subjects.

2.2.2 Exploratory objective

- To determine the number of subjects contracting SARS-CoV-2 during the 7 days after receiving their (last) dose.
- To assess the formation of Neumifil anti-drug antibodies (ADAs) after multiple-ascending intranasal doses in healthy subjects (Part B only).
- To assess plasma concentration of single- or multiple-ascending intranasal doses of Neumifil in healthy subjects to determine if intranasal administration results in systemic exposure.
- To assess the concentrations of cytokines and chemokines in nasal secretions before dosing and after multiple intranasal doses of Neumifil (Part B only).

2.3 Endpoints

2.3.1 Primary endpoints

Safety and tolerability:

Clinically significant changes in: vital signs (heart rate, blood pressure, respiratory rate, pulse oximetry, and temperature), 12-lead electrocardiogram (ECG), forced expiratory volume (FEV₁), forced vital capacity (FVC), physical examination, nasal examination, laboratory safety tests (haematology, biochemistry and urinalysis), tolerability questionnaire, number and severity of adverse events (AEs) and serious AEs. Safety endpoints will be assessed up to 7 days after dosing in Part A or up to 14 days after the last dose in Part B.

2.3.2 *Exploratory endpoint*

PD: SARS-CoV-2 infection test, done at screening, before the first dose, on Day 8 (Part B only), and at follow-up.

Immunogenicity: ADAs of Neumifil, as assessed by immunoglobulin A and G (IgA and IgG) concentration, derived from blood samples taken before the first dose and at follow-up (Part B only).

Plasma concentrations of Neumifil: Plasma concentrations of Neumifil after single doses on Day 1 in Part A, and after dosing on Days 1 and 7 in Part B.

Cytokine and chemokine concentrations in nasal secretions: Presence and concentration of cytokines and chemokines, measured by multiplex assay, in nasal wick samples collected on Day –1, Day 8, and at follow up (Part B only).

2.4 *Type of trial*

This is a Phase 1, single-centre, randomised, placebo-controlled first-time-in-human (FTIH) study in healthy subjects. The study is in 2 parts and will investigate single-ascending (Part A) and multiple-ascending (Part B) doses of Neumifil, administered intranasally.

2.5 *Trial design and methods*

2.5.1 *Part A*

Part A is a randomised, double-blind, placebo-controlled, single ascending dose study. Enrolment of up to 36 healthy subjects is planned, in up to 5 groups (Groups A1–A5). Groups A1–A3 will consist of 6 subjects each and Groups A4 and A5 will consist of 9 subjects each.

Subjects will receive a single intranasal dose of Neumifil or placebo. In Groups A1–A3, 4 subjects will receive Neumifil and 2 will receive matching placebo. In Groups A4 and A5, 6 subjects will receive Neumifil and 3 will receive matching placebo.

The planned dose levels are: 0.028 mg (Group A1), 0.085 mg (Group A2), 0.28 mg (Group A3), 0.885 mg (Group A4), and 2.8 mg (Group A5). Because Neumifil has never been given to humans before, each new ascending dose will be staggered via the use of sentinel subjects. It is intended that subsequent groups will receive higher doses. The dose will be escalated only if the safety and tolerability of the previous highest dose are acceptable, as determined by the Safety Review Group (SRG). Additional dose levels may be explored in up to 2 optional groups of 9 subjects (Groups A6 and A7).

Subjects will be screened within 35 days before their dose of trial medication. Subjects will be resident on ward from 1 day before their dose (Day –1) until about

24 h after dosing (Day 2). They will return for a follow-up visit 7–8 days after their dose (Day 8–9).

2.5.2 Part B

Part B is a randomised, double-blind, placebo-controlled, multiple ascending dose study.

Enrolment of up to 24 healthy subjects is planned, in up to 3 groups (Groups B1–B3) of 8 subjects each. Subjects will receive once-daily intranasal doses of Neumifil or placebo for 7 days. In each group, 6 subjects will receive Neumifil and 2 will receive matching placebo.

Part B can start before completion of Part A. The starting dose level (dose and dose regimen) for Group B1 will be decided after review of safety and tolerability data from at least 3 dose levels in Part A and will be no higher than a dose level that has previously been shown to cause no safety concerns in Part A (see section 8.5.3). Subsequent dose levels will be determined as described for Part A. An additional dose level may be explored in 1 optional group (Group B4).

Subjects will be screened within 35 days before their dose of trial medication. Subjects will be resident on ward from 1 day before their dose (Day –1) until about 24 h after their last dose (Day 8). Subjects will attend an outpatient visit at 7–8 days after their last dose (Days 15–16). They will then return for a follow-up visit at 13–15 days after their last dose (Days 21–23).

2.6 Trial population

- a **Total** Up to 60 healthy volunteers (up to 36 in Part A and up to 24 in Part B), excluding replacements
- b **Age** 18–60 years

c Inclusion criteria

Normotensive male or female volunteers, deemed healthy on the basis of a clinical history, physical examination, ECG, vital signs, and laboratory tests of blood and urine; body mass index (BMI; Quetelet index) in the range 18.0–30.9 kg/m²; non-smoker; FEV₁ and FVC ≥ 80%; agree to follow the contraception requirements of the trial (section 11); agree not to donate blood or blood products during the study and for 3 months after dosing; able to give fully informed written consent.

d Exclusion criteria

Positive tests for hepatitis B & C, human immunodeficiency virus (HIV); severe adverse reaction to any drug; sensitivity to trial medication; known allergy to tetracycline antibiotics; drug or alcohol abuse, or regular intake of > 14 units of alcohol weekly; evidence of smoking in the last 3 months; use of over-the-counter

medication (with the exception of paracetamol, or vitamin or nutritional supplements) during the 7 days, or prescribed medication (with the exception of hormone replacement therapy [HRT]), including oral contraceptives, during the 28 days, before the first dose of trial medication; receipt of a COVID-19 vaccine during the 7 days before the first dose of trial medication, or anticipate receiving a COVID-19 vaccine within the 7 days after a (final) dose of trial medication; participation in other clinical trials of unlicensed medicines, or loss of more than 400 mL blood, within the previous 3 months; vital signs and ECG measurements outside the acceptable range; clinically relevant abnormal findings at the screening assessment; acute or chronic illness; clinically relevant abnormal medical history (including psychiatric disease or cancer) or concurrent medical condition (including respiratory disease or illness); immune suppressed status, resulting from disease or medication; possibility that volunteer will not cooperate; females who are pregnant or lactating, or who are sexually active and not using a reliable method of contraception (section 11); objection by general practitioner (GP) to trial participation.

2.7 Assessments

The following assessments will be made.

2.7.1 Safety and tolerability

Laboratory assessments (haematology, biochemistry and urinalysis), physical examinations, 12-lead ECGs, vital signs (heart rate, blood pressure, respiratory rate, pulse oximetry and temperature), nasal examinations, FEV₁ and FVC will be done before and during dosing and frequently until the subject's last visit in each study part. Subjects will complete a tolerability questionnaire after each dose of Neumifil. AEs will be recorded from screening until the subject's last visit in each study part.

2.7.2 Pharmacokinetics

Blood samples for assay of Neumifil will be taken before and up to 3 h after dosing on Day 1 (Part A) and Days 1 and 7 (Part B).

6.1 Background

6.1.1 *Viral respiratory tract infections*

Viral respiratory tract infections (RTI) are of enormous global concern, particularly with the emergence of the coronavirus disease 2019 (COVID-19) pandemic (caused by severe acute respiratory syndrome coronavirus 2 [SARS-CoV-2]). Prophylactic approaches for viral RTIs, including coronaviruses such as SARS-CoV-2, influenza, and respiratory syncytial virus (RSV), are a significant unmet need.

Vaccines are available for individual strains of influenza. However, strain coverage is not universal, and hence the risk of low vaccine effectiveness continues year on year. Furthermore, there is low efficacy of influenza vaccines in the ageing population^{1,2}. Additionally, while vaccines are being rolled out against SARS-CoV-2, efficacy in the immunocompromised and immunosenescent population is not yet fully understood, and there is a significant risk of vaccine escape via viral mutations. Antivirals are also available to treat RTIs, but viral resistance remains a significant issue, and some antivirals (eg adamantanes) are no longer used for this reason. Therefore, a pan-viral prophylactic agent will complement the current prevention strategies.

6.1.2 *COVID-19*

The global pandemic of novel COVID-19 caused by SARS-CoV-2 began in Wuhan, China, in December 2019, and has since spread worldwide. As of 09 August 2021, there have been more than 203 million reported cases and over 4 million deaths across nearly 200 countries, and the numbers are still growing.

SARS-CoV-2 likely binds to epithelial cells in the nasal cavity. From the initial infection, the virus propagates and migrates down the respiratory tract along the conducting airways. For about 80% of the infected patients, the disease will be mild and mostly restricted to the upper and conducting airways; the most common symptoms at onset of illness are fever, new unproductive cough, fatigue, myalgia and loss of taste and smell. Unfortunately, about 20% of infected patients will develop pulmonary infiltrates and typically develop dyspnoea. Some of those patients will progress to a very severe disease phenotype which can result in hospitalisation, requirement for mechanical ventilation, and substantial morbidity and mortality.

Several vaccines have now been approved for use, either by individual countries or groups of countries, such as the European Union (EU). However, it is anticipated that it will take at least another 1–2 years until most of the world's population can be vaccinated. Also, vaccination may not achieve reliable protection for elderly or immune-compromised patients who also happen to be at highest risk for unfavourable clinical course of a SARS-CoV-2 infection. Last but not least, virus

mutation may result in viral escape from vaccine-induced immunity. It is therefore anticipated that there will be an ongoing need for efficacious therapeutic agents.

6.1.3 *Treating respiratory tract infections*

Targeting of the host glycome is a well-established mechanism for infectious diseases, including viral RTIs, to infect cells, and as such provides an avenue of strong therapeutic potential.

In the case of SARS-CoV-2, numerous studies^{3,4} support a major role for the virus-surface Spike protein to facilitate cell entry by binding to host-cell angiotensin-converting enzyme 2 (ACE2) receptors. [REDACTED]

Human influenza viruses, such as the 2009 pandemic H1N1 virus, recognize and bind to human α -2,6-linked sialic acid receptors in the upper respiratory tract. Avian influenza viruses, such as H5N1, predominantly recognize α -2,3-linked sialic acid receptors in the human lower respiratory tract. The human H7N9 influenza virus is unusual in recognizing both types of receptors and, therefore, has the possibility of sustained human-to-human transmission and pandemic potential⁷.

6.2 *Review of investigational medicinal product*

6.2.1 *Neumifil*

[REDACTED]

[figure not shown]
[REDACTED]

[REDACTED]

[figure not shown]
[REDACTED]

[REDACTED]

[REDACTED]

Figure 1: HEX17 hexavalent structure**Figure 2: Modifications made in the construction of HEX17 from parent CBM Sp2CBMTD**

6.2.2 *In vitro and in vivo pharmacology*

6.2.3 Safety pharmacology

A functional observation battery was used to assess neurotoxicity of Neumifil in a 28-day study in rats. No neurotoxicity was observed after repeated doses up to 1040 µg/animal/day, although a slight increase in the presence of pinna reflex was seen in both male and female treated animals. In a functional observation battery in primates Neumifil had no significant central nervous system (CNS) effects at repeated doses up to 1.65 mg/kg/day for 28 days.

Cardiovascular safety of Neumifil was tested in a 28-day repeat dose study in Cynomolgus monkeys. Animals received repeated doses up to 1.25 mg/kg/day, and there were no changes in ECG, or in diastolic and systolic blood pressure.

Standalone respiratory safety studies have not been done. The pharmacology of Neumifil does not suggest any respiratory risk, and no significant lung pathology has been noted in efficacy studies in mice and rats, or in dose-finding studies. Specific respiratory observations were made during the 28-day repeat dose study in primates. There were no changes in respiratory signs (rhinorrhoea, sneezing, coughing, abnormal breath sounds, respiratory rate, and breathing depth).

6.2.4 Pharmacokinetics

The absorption and pharmacokinetics of Neumifil have been studied after single intravenous and intranasal doses in rats. Neumifil 0.5 mg/kg given intravenously yielded mean C_{max} 1240 ng/mL, $AUC_{(0-inf)}$ 2360 ng.h/mL, and terminal half-life 24.1 h (range 9.29–46.0 h). Pharmacokinetic parameters could not be calculated after intranasal administration of 4 mg/kg Neumifil, because plasma concentrations were above the lower limit of reliable quantification (LRQ: 25.0 ng/mL) in only a single sample at 2 h post dose (plasma concentration 42.8 ng/mL). Bioavailability of intranasal Neumifil was therefore considered to be < 5%.

Very low plasma concentrations of Neumifil were detected during the 28-day repeated dose study in rats. The paucity of samples with quantifiable concentrations of Neumifil precluded any calculation of (pharmacokinetic) PK parameters, but systemic exposure was clearly minimal after repeated intranasal administration of doses up to 1040 µg/day. Given the low plasma concentrations of Neumifil after intranasal dosing, its distribution has not been studied.

It is anticipated that intranasal Neumifil (a protein) will be broken down in the nasal mucosa by local peptidases to yield oligopeptides and free amino acids. Thus, further investigation of Neumifil metabolism is deemed unnecessary.

6.2.5 Toxicology

In the rat dose-range finding study, systemic exposure to Neumifil could not be determined because too few plasma samples had concentrations above LRQ. Rats received intranasal doses up to 1000 µg/day for 7 days, and there were no treatment-related deaths or significant clinical observations. However, some female rats had a slight decrease in body weight gain (average 3%), attributed to decreased food consumption. The maximum tolerated dose was 1000 µg/animal/day.

In the pivotal Good Laboratory Practice (GLP) 28-day repeated dose toxicity study in rats, animals received intranasal doses of 520, 780, and 1040 µg/animal/day, but again few samples had plasma Neumifil concentrations above LRQ. The following pharmacokinetic parameters were estimated for Day 28: C_{max} 123 ng/mL; t_{max} 2 h; and AUC 381 ng.h/mL. No animal died, but significant weight loss occurred at the 2 highest dose levels (6% in males and 7% in females). That adverse effect was reversible after 2 weeks' recovery. Abnormal respiratory sounds (loud breathing and/or respiratory crackles) were observed at all dose levels but remitted after dosing was stopped. Mild to moderate inflammatory and reactive changes in the nasal mucosa, associated with polymorphonuclear cell infiltration and goblet cell proliferation, were found in all treatment groups but were considered adverse only at the mid and top dose levels. Inflammatory changes were noted also in respiratory tissues (larynx, trachea, bronchi and bronchioles) at the 2 highest dose levels of Neumifil, but animals recovered fully after 2 weeks. The no observed adverse effect level (NOAEL) in rats after 4 weeks' dosing was 2.5 mg/kg/day.

In a non-GLP dose-range finding study, Cynomolgus monkeys received doses up to 1.25 mg/kg/day for 7 days. There were no treatment-related deaths or significant clinical findings.

Doses of 0.8, 1.20 and 1.65 mg/kg/day were tested in a GLP 28-day repeated dose Cynomolgus monkey toxicity study. All plasma concentrations of Neumifil were below LRQ. There were no deaths, and no effects related to the test item. ADA analysis showed weak seroconversion in 4 animals, but ADA titres were similar to those in untreated animals, so Neumifil was of low immunogenicity. The NOAEL in Cynomolgus monkeys after 4 weeks' dosing was 1.65 mg/kg/day.

6.2.6 Pharmacodynamics

Doses of up to 100 µg *Sp2CBMTD* were administered to BALB/c mice in order to investigate the potential mechanism of action of the parent family of HEX17, and its efficacy in preventing and treating infection with the influenza virus. *Sp2CBMTD* was either administered prophylactically to mice that were then challenged with a lethal dose of the virus, or administered after the viral challenge. As well as promoting animal survival (80–100% when administered prophylactically, or 40% after exposure to the virus), cytokine analysis revealed that *Sp2CBMTD* stimulated a proinflammatory response when given as a prophylactic. [REDACTED]

A horizontal bar chart consisting of four solid black bars of increasing length from left to right. The first bar is the shortest, followed by a slightly longer bar, then a much longer bar, and finally the longest bar on the far right. The bars are separated by small gaps.

██████████ Neumifil has low to minimal risk of generating viral resistance because of its host- and viral-targeting modes of action. Neumifil's *in vitro* and *in vivo* animal data, potential pan-viral efficacy, and toxicology profile makes it suitable for progression to a FTIH study.

6.3 Rationale for the trial

This FTIH study will investigate the safety and tolerability of Neumifil after single and repeated intranasal administration in a randomised, double-blind, placebo-controlled trial. The results of this study will be used to select doses for subsequent trials.

6.4 Rationale for choice of dose(s)

6.4.1 Starting dose

In the absence of the viral target, the minimum anticipated biological effect level (MABEL) is not relevant in calculating the starting dose. Instead, the safety-focused no observed adverse effect (NOAEL) approach was used.

As is typical for molecules dosed intranasally⁸, the margin of safety was calculated based on both systemic and local toxicity. The Human Equivalent Dose (HED) was not corrected for body surface area, as HEX17 is a recombinant protein of molecular weight 162 kD, and proteins are typically normalised on a mg/kg basis without allometric scaling.

The NOAELs in the 28-day GLP toxicology studies in rats and Cynomolgus monkeys were 2.5 mg/kg/day and 1.65 mg/kg/day, respectively. The monkey is the more sensitive species and is also the more relevant for humans with respect to nasal structure and toxicity⁹, so was used to calculate safety margins. The margins of safety for the planned first dose and maximum intended clinical dose, calculated for systemic toxicity (mg/kg/day) and local toxicity (mg/kg/cm²) are shown, respectively, in Table 1 and Table 2.

Table 1 Calculation of margins of safety for Neumifil, based on mg/kg bodyweight

	Monkey	Planned first clinical dose (28 µg)	Maximum intended clinical dose (885 µg)
Dose at NOAEL	1650 µg/kg/day	n/a	n/a
HED (µg/kg/day; calculated for a 60 kg person)	n/a	0.46 µg	14.75 µg
MoS on µg/kg/day basis	n/a	3587 fold	112 fold

HED: Human equivalent dose; MoS: Margin of Safety; NOAEL: No Observed Adverse Effect Level

Table 2 Calculation of margins of safety for Neumifil, normalised by nasal surface area

	Monkey	Planned first clinical dose (28 µg)	Maximum intended clinical dose (885 µg)
Dose at NOAEL	1650 µg/kg/day	n/a	n/a
HED (µg/kg/day; calculated for a 60 kg person)	n/a	0.46 µg	14.75 µg
Dose normalised by species-specific nasal surface area ¹ (µg/kg/cm ²)	26.78	0.0025 µg	0.081 µg
MoS on µg/kg/cm ² basis	n/a	10,600 fold	331 fold

HED: Human equivalent dose; MoS: Margin of Safety; NOAEL: No Observed Adverse Effect Level

¹ 61.6 cm² in monkey; 181 cm² in human

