6.5 Assessment and management of risk

Any safety risk to study participants is mitigated by the following considerations.

- Data from pre-clinical studies suggest that Neumifil is devoid of any significant CNS or cardiovascular effects. Although standalone respiratory safety studies have not been performed, the pharmacology of Neumifil does not suggest any respiratory risk, and no significant lung pathology has been noted in efficacy studies in mice and rats, or in dose range finding studies.
- In the pivotal GLP 28-day repeated dose toxicity study in rats, significant weight loss was observed in animals at the two highest dose levels: 780 and 1040 µg/animal/day (6% in male and 7% in female animals). This adverse effect was found to be reversible after 2 weeks recovery.
- Abnormal respiratory sounds (loud breathing and/or respiratory crackles) were observed at all doses levels, and this ceased after dosing was stopped.
- Mild to moderate inflammatory and reactive changes were found in the nasal mucosa and respiratory tissues, in animals receiving the two highest dose levels of Neumifil, although animals fully recovered after 2 weeks. The NOAEL in rats following 4 weeks of dosing was 2.5 mg/kg/day.
- The available pre-clinical toxicity data indicate an acceptable safety profile for Neumifil. The NOAEL in the Cynomolgus monkey corresponds to a HED of 0.46 µg in humans with a body weight of 60 kg. The proposed starting dose in Part A of 0.028 mg provides a 3587 fold and 10,600 fold margin of safety based on bodyweight or when normalised by nasal surface area respectively. The maximum selected dose provides a 112 and 331 fold margin of safety when calculated according to bodyweight, or when normalised by nasal surface area, respectively. In addition, the starting dose selected for Group B1 in Part B (multiple ascending dose part of the study) will be no higher than the highest dose that caused no safety concerns in Part A.
- Dose escalation will take place only after safety and tolerability data from preceding dose level(s) have been reviewed. There will be an appropriate interval between sequential groups, to allow for review of those data. Dose escalation will be halted if the stopping criteria are met (see section 8.4.2).
- As Neumifil has never been given to humans before, each new ascending dose will be staggered: sentinel subject will be dosed first, and the remaining subjects will be dosed at least 23 h later.

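### Table 2 divides a per-kilogram dose by nasal area, so the 10,600-fold and 331-fold local safety margins are too large by a factor of 60 divided by the monkey's weight in kg

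*Combined protocol and SAP*

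**What the plan says.** Section 6.4.1 of the protocol takes the no-observed-adverse-effect level (NOAEL) of the 28-day monkey study, "1650 µg/kg/day", as the reference dose and gives two margins: those "calculated for systemic toxicity (mg/kg/day) and local toxicity (mg/kg/cm²) are shown, respectively, in Table 1 and Table 2". The human dose is expressed per kg for a 60 kg person: 0.46 µg/kg at 28 µg and 14.75 µg/kg at 885 µg.

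Table 2 then divides each per-kg dose by the nasal surface area of the species, which its footnote gives as "61.6 cm² in monkey; 181 cm² in human". The results are 26.78 µg/kg/cm² for the monkey and 0.0025 and 0.081 µg/kg/cm² for the human doses. The local margins follow as 10,600-fold and 331-fold.

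Section 6.5 relies on these figures among the points that mitigate risk: the starting dose "provides a 3587 fold and 10,600 fold margin of safety based on bodyweight or when normalised by nasal surface area respectively". It quotes 112-fold and 331-fold for the maximum dose. No section gives a dose in µg per cm², the monkeys' body weight, or a reason for keeping the per-kg term in the local calculation.

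**The concern.** Local toxicity of a nasal product depends on how much drug lies on each cm² of mucosa. Once the actual nasal area is in the formula, body weight has no further part to play. Under Table 2's method, two people with the same nose and the same 28 µg dose, one of 60 kg and one of 120 kg, would have local margins that differ by a factor of two, although their mucosal exposure is identical.

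The order of the two margins is a further sign. The human nose has 2.9 times the area of the monkey's, whereas a 60 kg human outweighs any plausible cynomolgus monkey by much more than that. An area-based margin should therefore be smaller than the body-weight margin, yet Table 2 shows it 2.9 times larger.

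The local margin is the one that matters most here. Sections 6.2.4 and 6.2.5 describe minimal systemic exposure after nasal dosing, with all plasma concentrations in the 28-day monkey study below the quantification limit. Many of the rat findings were in the airway. Nasal mucosal changes "were found in all treatment groups but were considered adverse only at the mid and top dose levels", and inflammation of the larynx, trachea, bronchi and bronchioles was seen at the two highest doses. In a first-in-human trial, an inflated local margin misinforms the investigator, the regulator and the ethics committee.

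**Working it through.** **Inputs.** From section 6.4.1 and Tables 1 and 2: monkey NOAEL 1650 µg/kg/day; nasal areas 61.6 cm² (monkey) and 181 cm² (human); human weight 60 kg; doses 28 µg and 885 µg. From sections 6.4.2 and 8.1.1: maximum permitted dose 2.8 mg. Monkey weight W is not given. I use 3–5 kg as the main assumption and 2–8 kg as a wider range.

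**Step 1: reproduce the plan's figures.** Stated method:

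margin = (NOAEL / 61.6) / ((dose / 60) / 181)

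- Monkey: 1650 / 61.6 = 26.79 µg/kg/cm².
- 28 µg: (28/60)/181 = 0.00258, giving 10,389 unrounded. Rounding the human dose to 0.46 µg/kg gives 10,540; using 26.78/0.0025 gives 10,712. Stated: 10,600.
- 885 µg: 14.75/181 = 0.0815, giving 329. Using 26.78/0.081 gives 331. Stated: 331.

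Both stated figures are reproduced to within about 2%, with the per-kg term kept in. Table 2 is Table 1 multiplied by 181/61.6 = 2.94: 3587 × 2.94 is about 10,540, and 111.9 × 2.94 is about 329.

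**Step 2: dose per unit of mucosa.**

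margin = (NOAEL × W / 61.6) / (dose / 181)

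- Monkey at the NOAEL: 26.79 × W µg/cm².
- Human: 28/181 = 0.155; 885/181 = 4.89; 2800/181 = 15.47 µg/cm².
- Margins: 26.79W/0.155 = 173×W; 26.79W/4.89 = 5.5×W; 26.79W/15.47 = 1.73×W.

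| W (kg, assumed) | 28 µg (stated 10,600) | 885 µg (stated 331) | 2.8 mg (not stated) | Overstatement 60/W |
|---|---|---|---|---|
| 2 | 346 | 11.0 | 3.5 | 30 |
| 3 | 519 | 16.4 | 5.2 | 20 |
| 5 | 866 | 27.4 | 8.7 | 12 |
| 8 | 1385 | 43.8 | 13.9 | 7.5 |

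**Step 3: size of the overstatement.** The ratio of the two formulas is

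(NOAEL × 60 × 181)/(dose × 61.6) ÷ (NOAEL × W × 181)/(dose × 61.6) = 60/W.

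It does not depend on the dose or the nasal areas, and it exceeds 1 whenever W is below 60 kg.

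**Step 4: which margin is limiting.** The corrected local margin divided by the body-weight margin is (W/60) × (181/61.6) = W/20.4. The local margin is therefore the smaller of the two for any monkey under about 20.4 kg, the reverse of what Tables 1 and 2 show.

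**The case against.** The strongest reply is that this is a choice of metric and not a slip. The protocol declares its unit openly, the division follows that unit, and a published source is cited for calculating both systemic and local margins. But declaring a unit does not make it a measure of local exposure. A local margin that rises with the subject's body weight while the dose and the nose stay the same is wrong for its stated purpose, and the protocol offers no justification for it.

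Several other points stand and limit the consequences:

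- Every corrected margin expressed as a number rests on an assumed monkey weight. Only the factor 60/W comes from the documents, and the reversal of order in Step 4 needs W below 20.4 kg.
- The monkey NOAEL was the highest dose in the 28-day study, with no effects related to the test item (section 6.2.5). The dose that would cause local harm in monkeys may be higher. It is also a 28-day figure, set against a single dose in Part A and 7 days (at most 14) in Part B.
- The rat findings had recovered after 2 weeks, and Table 2 contains no rat figure. They show why the local margin matters but play no part in the calculation.
- No escalation or stopping rule is tied to this margin. Sentinel dosing, the 3.5-fold cap on dose steps, the Safety Review Group's review of nasal examination, FEV₁ and tolerability, and the stopping criteria all operate regardless.
- Table 2 states no margin at 2.8 mg, so that column supplies a missing figure and does not correct a stated one.

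These points bear on how alarming the corrected margins are. They do not make 10,600 and 331 correct.

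**Conclusion.** The concern holds: Table 2 is wrong as written. The local margins in sections 6.4.1 and 6.5 are overstated by exactly 60/W, which is 12- to 20-fold if the monkeys weighed 3–5 kg and 7.5- to 30-fold for 2–8 kg. The direction is certain for any monkey under 60 kg.

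The starting dose keeps a margin in the hundreds or more over the assumed range, so this does not show that it is unsafe. The change is material higher up: tens and not hundreds at 885 µg, and about 3.5 to 14 at the 2.8 mg that the protocol permits. It must be fixed because a first-in-human risk assessment for an intranasal product presents its most relevant margin as roughly ten times more favourable than it is.

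**What to change.** Recompute Table 2 as total dose in µg divided by nasal surface area for both species, using the actual body weights from the 28-day monkey study. Show the starting dose, 885 µg and the permitted maximum of 2.8 mg. Replace the 10,600-fold and 331-fold figures in section 6.5, change the local unit in section 6.4.1 to µg/cm², and revise the dose rationale to state which margin is limiting and why the remaining margin at 2.8 mg is acceptable. That text can fairly say that the NOAEL was the top dose tested and point to the sentinel and escalation safeguards.

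The cost is a recalculation from data the sponsor should hold, plus an amendment to the protocol text. The margins will look less favourable.
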